#### B. Determination of Patients/Data for Analysis

The analysis will be performed on patients in the analysis cohort. Furthermore, it is necessary that patient have measurements during MultiSpot SEQ pacing and during the respective BiV configuration used for comparison.

### 7.9.3. Secondary Objective #1

Compare the positive LV dP/dt max from a MultiSpot-SEQ LV pacing configuration to a MultiSpot-SYN LV pacing configuration in patients undergoing a research study, an EP exploratory procedure or CRT-implant using the contractility parameter positive LV dP/dt max.

#### 7.9.3.1. Hypothesis

It is hypothesized that MultiSpot pacing sequentially (from apex to mid and then to base) is non-inferior to MultiSpot pacing simultaneously.

The null and alternative hypotheses are thus:

$$H_0: \Delta_{\text{MultiSpot SEQ}} - \Delta_{\text{MultiSpot SYN}} \leq -3\% \text{ (MultiSpot SEQ inferior)}$$

$$H_1: \Delta_{\text{MultiSpot SEQ}} - \Delta_{\text{MultiSpot SYN}} > -3\% \text{ (MultiSpot SEQ non-inferior)}$$

### 7.9.3.2. Endpoint Definition

The endpoint is the same as for the primary objective #1, i.e., % change LV dP/dt max from baseline (AAI pacing).

### 7.9.3.3. Analysis Methods

#### A. Statistical Methodology

Statistical analysis will use the methods described for the primary objective 1, with single spot LV pacing configuration (standard BiV) replaced by MultiSpot-SEQ LV pacing.

Inferiority testing will be performed one-sided at a significance level of 0.025. Non-inferiority of MultiSpot SEQ to MultiSpot SYN will be declared if the lower limit of a two-sided 95% confidence interval for the mean difference between MultiSpot SEQ and SYN does not fall below -3%. Superiority testing will be performed two-sided at a significance level of 0.05.

Results for non-inferiority testing will be summarized in a table similar to the table below:

**Table 12: Comparison between MultiSpot SEQ and MultiSpot SYN (non-inferiority testing)**

Comparison	Number of Subjects	Difference in % change LV dP/dt max	95 % Confidence interval	P-value
MultiSpot SEQ– MultiSpot SYN	N	x.xx	x.xx – x.xx	x.xxxx

Results for superiority testing will be summarized in a table similar to the below if non-inferiority is significant:

**Table 13: Comparison between MultiSpot SEQ and MultiSpot SYN (superiority testing)**

Comparison	Number of Subjects	Difference in % change LV dP/dt max	95 % Confidence interval	P-value
MultiSpot SEQ– MultiSpot SYN	N	x.xx	x.xx – x.xx	x.xxxx

#### B. Determination of Patients/Data for Analysis

The analysis will be performed on patients in the analysis cohort. Furthermore, it is necessary that patient have measurements during MultiSpot SEQ and SYN pacing.

### 7.9.4. Secondary Objective #2

Correlate the (non)invasive measures (blood pressure, electrocardiographic mapping and RV/LV EGM timings) obtained during the different pacing configurations to the positive LV dP/dt max measures obtained.

The purpose of this objective is to evaluate the feasibility of other measures, in particular non-invasive measures, to assist with optimal lead placement and pacing sequence.

#### 7.9.4.1. Hypothesis

There are no hypotheses specified.

#### 7.9.4.2. Endpoint Definition

The following table summarizes measures collected for this objective and the tool which will be used during the EP study to acquire them. All these measures will be collected during the EP study and derived using algorithms developed by the scientists. In the table below it is further indicated whether these measurements are invasive or non-invasive. The final list of secondary endpoints will be specified at study end before the statistical analysis.

**Table 14: Measures**

Endpoint	Invasive/non-invasive	Tool
LV dP/dt max (mmHg/sec)	Invasive	LV catheter
Diastolic blood pressure (mmHg)	Invasive	Blood pressure transducer
Systolic blood pressure (mmHg)	Invasive	Blood pressure transducer
Diastolic blood pressure (mmHg)	Non-invasive	Finger volume clamp
Systolic blood pressure (mmHg)	Non-invasive	Finger volume clamp
QRS duration (msec)	Non-invasive	Surface ECGs
RV-LV timing (msec)	Invasive	Electrocardiogram
Q-LV interval (msec)	Invasive	Electrocardiogram and surface ECGs

LV dP/dt max and blood pressures are collected during the pacing protocol. The non-invasive blood pressures are collected optionally. RV-LV timing and Q-LV are collected during threshold testing and setup before the start of the pacing protocol.

The Q-LV interval is defined as the time from the onset of the QRS width of the surface ECG to the first large positive or negative peak of the LV electrogram (EGM) during a cardiac cycle. Percentage Q-LV (% Q-LV) will be calculated as the absolute Q-LV/QRS duration. Since there are three LV electrodes, the Q-LV interval can be determined for the apical, mid and basal LV electrode position.

The RV-LV timing gives the interval between intrinsic deflection of RV EGM and LV EGM. Since there are three LV electrodes, the RV-LV interval can be determined for the apical, mid and basal position. The following types of RV-LV timing (or LV-LV timing) might be collected:

- RV paced – LV sensed
- RV sensed – LV sensed
- LV paced – LV sensed
- LV paced – RV sensed

max	SBP			

## B. Determination of Patients/Data for Analysis

The analysis will be performed on patients in the analysis cohort.

### 7.9.5. Secondary Objective #3

Evaluate the (non)invasive measures ability to identify the pacing configuration with the highest positive LV dP/dt max.

#### 7.9.5.1. Hypothesis

There are no hypotheses specified.

#### 7.9.5.2. Endpoint Definition

All these measures will be collected longitudinally during the EP study and derived using algorithms developed by the scientists/engineers.

The following table summarizes measures collected for this objective and the tool which will be used during the EP study to acquire them. All these measures will be collected during the EP study and derived using algorithms developed by the scientists. In the table below it is further indicated whether these measurements are invasive or non-invasive. The final list of secondary endpoints will be specified at study end before the statistical analysis.

**Table 16: Measures**

Endpoint	Invasive/non-invasive	Tool
LV dP/dt max (mmHg/sec)	Invasive	LV catheter
Diastolic blood pressure (mmHg)	Invasive	Blood pressure transducer
Systolic blood pressure (mmHg)	Invasive	Blood pressure transducer
Diastolic blood pressure (mmHg)	Non-invasive	Finger volume clamp
Systolic blood pressure (mmHg)	Non-invasive	Finger volume clamp
QRS duration (msec)	Non-invasive	Surface ECGs

Q-LV timings and RV-LV timings can only be determined for BiV apical, BiV basal, and BiV mid configurations but not for the MultiSpot configurations since the timings are based on the time that the electrical signal takes from the Q-wave resp. RV EGM to the individual LV EGMs, i.e., LV1 EGM for electrode 1 (apical), LV2 EGM for electrode 2 (basal), and LV3 EGM for electrode 3 (LV3 EGM). As a consequence, these measures are not relevant for this objective. For LV dP/dt max and blood pressures, the analysis will be based on % changes from baseline.

**7.9.5.3. Statistical Methodology**

**A. Statistical Methodology**

A categorical variable of the best pacing configuration per patient will be calculated (the configuration that achieves the largest dP/dt value) and the agreement with each (non)invasive evaluation of best pacing configuration (also derived into a categorical variable) will be evaluated and tested with an unweighted Kappa statistic.

The following steps will be performed for analysis. These steps will be repeated for each endpoint.

1. Regression model per patient (see primary objective #1)
2. Use the parameter estimates from regression model to obtain predicted maximum response and corresponding best AV delay per configuration (see primary objective #1)
3. Determine the best configuration for each patient, i.e., the configuration with largest maximum response
4. Create a categorical variable which contains for each patient the best configuration

In the final step, we will evaluate and test the agreement between these ratings based on dP/dt max and the other endpoints using an unweighted Kappa statistic. The kappa statistics can be seen as a correlation between categorical variables. Our categorical variables give here the best configuration based on the different measurements. The kappa statistic adjusts for the agreement which might happen by chance. A kappa statistic of 1 indicates perfect agreement between the variables while a kappa statistic of 0 indicates that the agreement is due to chance. A kappa statistic lower than 0 indicates that the agreement is less than the agreement which might happen due to chance.

The results will be summarized into a table similar to the table given below. The total numbers x will be given, where the best configuration was chosen to be one configuration based on dP/dt max and another configuration or the same configuration based on the second measure. Furthermore, cell percentage, row percentage, column percentages will be indicated per xx.x %. The last cell will give the total number of subjects available for the analysis.

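### SAP 7.9.5.3 applies one maximum rule to every endpoint, so for QRS duration the widest predicted QRS is labelled the best configuration

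*SAP*

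**What the plan says.** SAP 7.9.5.3 finds the best configuration per patient on LV dP/dt max and on each other measure, then compares the two choices with an unweighted kappa. Of the listed steps it says "These steps will be repeated for each endpoint". Step 2 reads "Use the parameter estimates from regression model to obtain predicted maximum response and corresponding best AV delay per configuration", and Step 3 reads "Determine the best configuration for each patient, i.e., the configuration with largest maximum response". Step 2 refers back to primary objective 1, where SAP 7.9.1.3 also describes the best AV delay as the one that maximises the prediction.

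Table 16 lists the endpoints of this objective and includes QRS duration, in msec. The text below it removes only the Q-LV and RV-LV timings, so QRS stays. On scale it says "For LV dP/dt max and blood pressures, the analysis will be based on % changes from baseline", which leaves QRS in msec with no stated transformation or sign. Protocol H.1.5 gives no direction for any comparator measure.

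On interpretation, SAP 7.9.5.3 says "A kappa statistic lower than 0 indicates that the agreement is less than the agreement which might happen due to chance".

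**The concern.** A maximum is the right operator for LV dP/dt max, because the objective is to find the configuration with the highest value. It does not automatically suit every other measure. The same operator applied to QRS duration picks the widest predicted QRS twice: first over AV delay within a configuration, then across configurations.

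Secondary objective 3 asks whether other measures can point to the configuration with the highest dP/dt max. The study also aims to judge non-invasive sensors as aids to lead placement and pacing sequence. QRS is one of three non-invasive measures in Table 16, and the other two (finger-clamp pressures) are collected optionally according to SAP 7.9.4.2. For some patients QRS may therefore be the only non-invasive measure available. If narrower QRS goes with higher dP/dt max, the planned kappa would report an informative measure as worse than chance.

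**Working it through.** The plan gives no figure for this point. The kappa values in SAP Tables 18 and 19 are sample output and do not bear on it. The check has a textual part and a numerical part.

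**1. What the rule selects.** Take one hypothetical patient with predicted QRS = b + 0.05·g + 0.002·g², where g is the AV offset in ms (-60 to +60). Let b = 160, 155, 158, 140 and 145 ms for BiV apex, BiV mid, BiV base, SYN and SEQ. All values are assumed.

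- Rule as written: each curve peaks at g = +60, which adds 0.05·60 + 0.002·3600 = 3.0 + 7.2 = 10.2 ms. The maxima are 170.2, 165.2, 168.2, 150.2 and 155.2 ms. The largest belongs to BiV apex, the widest QRS.
- Minimum rule: on a 1 ms grid each curve is lowest at g = -13, which adds -0.65 + 0.338 = -0.312 ms. The smallest minimum is 139.7 ms, for SYN.

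Expressing QRS as plain % change would not help, since the largest value is then the greatest widening.

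**2. Why a sign change does not repair the result.** Kappa = (p_o - p_e)/(1 - p_e), where p_o is observed and p_e chance agreement. With five equally frequent configurations p_e = 5 × 0.2² = 0.20. The lowest possible value, at p_o = 0, is (0 - 0.20)/(1 - 0.20) = -0.25. A perfect inverse relation therefore gives -0.25 under the written rule and 1.00 under the reversed rule.

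**3. Size.** Assumptions: five exchangeable configurations per patient, and correlation -r between QRS and dP/dt max across configurations. The documents give no r. For example, at r = 0.3 simulated agreement is 0.109 under the written rule and 0.314 for narrowest QRS, so kappa is (0.109 - 0.20)/0.80 = -0.11 and (0.314 - 0.20)/0.80 = 0.14.

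| r | Kappa, narrowest QRS | Kappa, rule as written |
|---|---|---|
| 0 | 0.00 | 0.00 |
| 0.3 | 0.14 | -0.11 |
| 0.5 | 0.26 | -0.17 |
| 0.7 | 0.42 | -0.22 |
| 1.0 | 1.00 | -0.25 |

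If the premise has the wrong sign (correlation +0.3), the two columns become -0.11 and 0.14.

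**4. Adding the AV-delay search.** A second model fitted a quadratic per configuration over the five AV offsets. It assumed a level SD of 1, noise SD of 0.5 averaged over four repetitions, an optimum offset with SD 20 ms shared by both measures, and curvatures of 0.5 or 1 SD (dP/dt) and 0, 0.5 or 1 SD (QRS) at 60 ms.

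| r | Narrowest QRS | As written |
|---|---|---|
| 0.3 | 0.14 | -0.09 to -0.11 |
| 0.5 | 0.25 to 0.26 | -0.14 to -0.17 |
| 0.7 | 0.40 | -0.19 to -0.22 |
| 1.0 | 0.82 | -0.23 to -0.25 |

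**5. At the planned size.** In 10,000 simulated trials of 40 patients under the model of step 3, kappa was below 0 under the written rule in 95% to 96% of trials at r = 0.3 and 99.8% at r = 0.5. Choosing the narrowest QRS, the shares were 5% to 6% and 0.3%. The ranges reflect repeated runs.

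**The case against.** The strongest reply is that this is loose wording and not a plan to call the widest QRS best. The opening sentence of SAP 7.9.5.3 ties the largest value to dP/dt only, and the numbered steps may have been carried over from primary objective 1. Response and best could be read as meaning the favourable direction, and a competent analyst might reverse QRS unprompted. The measures are derived by the study scientists, so QRS could reach the statistician already expressed as shortening. Some code and methods text is blacked out and could contain a sign rule. QRS could also leave the list, since "The final list of secondary endpoints will be specified at study end before the statistical analysis".

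These points limit the weight of the concern but do not remove it. No visible text reverses the direction, and the visible description of the redacted AV-delay code also says maximum. The promise of a final list does not mention direction. If the direction stays open, it could be chosen after the kappas are seen.

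Other objections stand in part. No document says that narrower paced QRS goes with higher dP/dt max. Every correlation above is assumed, and exchangeable configurations do not match the advantage the SAP expects for SYN and SEQ. Giving those two a 1 SD advantage moves the written-rule kappa at r = 0.3 to between -0.06 and -0.13: the sign is the same but the size differs. A kappa below 0 is also not always a striking result. At n = 40 and r = 0.3, about 24% of simulated values lay more than 1.96 null standard errors below 0. Finally, the correlations of secondary objective 2 keep their sign and might reveal an inverse relation, but they do not correct the kappa.

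**Conclusion.** The concern holds. The SAP states an explicit rule, extends it to every endpoint and keeps QRS duration among them; followed as written, it labels the widest predicted QRS as best. That reading rests on the text alone.

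The harm depends on the assumption that narrower QRS accompanies higher dP/dt max. Under it, kappa for QRS is negative where it should be positive: about -0.11 against 0.14 at r = 0.3, and -0.17 against 0.26 at r = 0.5. These sizes are illustrative.

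The reach is limited to the QRS result of one secondary objective that carries no hypothesis. The primary objectives and the sample size are untouched. It should be corrected before analysis, because the reported kappa would otherwise not answer the question secondary objective 3 asks about QRS.

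**What to change.** Before the data are analysed, state in Steps 2 and 3 of SAP 7.9.5.3 the scale and direction for each Table 16 endpoint, including diastolic pressure. Keep the predicted maximum for LV dP/dt max. For QRS duration, take the predicted minimum over AV delay and then the configuration with the smallest minimum. Alternatively, define the QRS response as shortening from baseline and leave the maximum rule unchanged. The final endpoint list promised in SAP 7.9.5.2 is a natural place to record this.

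The cost is one sentence in the SAP and a sign change in the code. No new data are needed.

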**Table 17: Best configuration**

	Best configuration based on dP/dt max					Total
	BiV proximal	BiV distal	BiV mid	MultiS pot SYN	MultiS pot SEQ	

	BiV proximal	x	x	x	x	x	x
		xx.x %	xx.x %	xx.x %	xx.x %	xx.x %	xx.x %
		xx.x %	%	%	%	xx.x %	
		xx.x %	xx.x %	xx.x %	xx.x %	xx.x %	xx.x %
			%	%	%		
			xx.x %	xx.x %	xx.x %		
			%	%	%		
	BiV distal	x	x	x	x	x	x
		xx.x %	xx.x %	xx.x %	xx.x %	xx.x %	xx.x %
		xx.x %	%	%	%	xx.x %	
		xx.x %	xx.x %	xx.x %	xx.x %	xx.x %	xx.x %
			%	%	%		
			xx.x %	xx.x %	xx.x %		
			%	%	%		
Based on non-invasive measure	BiV mid	x	x	x	x	x	x
		xx.x %	xx.x %	xx.x %	xx.x %	xx.x %	xx.x %
		xx.x %	%	%	%	xx.x %	
		xx.x %	xx.x %	xx.x %	xx.x %	xx.x %	xx.x %
			%	%	%		
			xx.x %	xx.x %	xx.x %		
			%	%	%		
	MultiSpot SYN	x	x	x	x	x	x
		xx.x %	xx.x %	xx.x %	xx.x %	xx.x %	xx.x %
		xx.x %	%	%	%	xx.x %	
		xx.x %	xx.x %	xx.x %	xx.x %	xx.x %	xx.x %
			%	%	%		
			xx.x %	xx.x %	xx.x %		
			%	%	%		
	MultiSpot SEQ	x	x	x	x	x	x
		xx.x %	xx.x %	xx.x %	xx.x %	xx.x %	xx.x %
		xx.x %	%	%	%	xx.x %	
		xx.x %	xx.x %	xx.x %	xx.x %	xx.x %	xx.x %

		%	%	%		
		XX.X	XX.X	XX.X		
		%	%	%		
Total	x	x	x	x	x	N
	XX.X %	XX.X	XX.X	XX.X	XX.X %	XX.X %
		%	%	%		

**Table 18: Kappa statistic**

Statistic	Value	Approximated standard error	95 % Confidence Limits	
Simple Kappa	0.3449	0.0724	0.2030	0.4868

Sample size = 40

**Table 19: Test of H0: Kappa = 0**

Statistic	Value	Approximated standard error under H 0	Z-statistic	P-value (One-sided Pr > Z)	P-value (Two-sided Pr >  Z )
Simple Kappa	0.3449	0.0612	5.6366	<.0001	<.0001

Sample size = 40

**B. Determination of Patients/Data for Analysis**

The analysis will be performed on patients in the analysis cohort.

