Pacing electrodes (cardiac leads or EP catheters) will be placed in the right atrium (RA) and right ventricle (RV). The coronary sinus will be cannulated, a venogram will be obtained and target vessels for LV stimulation will be identified. An EP-catheter ("Multi-electrode lead") or LV lead will be used for LV pacing. The temporary LV pacing electrodes (e.g. EP catheter or LV lead) will be inserted into the coronary sinus and then sequentially into the suitable target vein. Targeted myocardial regions for LV lead/catheter placement are: lateral or posterolateral vein (standard vein), and the vein displaying the most promise to reach the true LV apical position (to be anticipated the anterior vein). To reach the most LV apical position small EP-catheters or pacing guide wire will be used.

Pacing will be performed at up to three electrodes simultaneously or sequentially within the (standard) vein(s) (MultiSpot-SYN and MultiSpot-SEQ), covering the LV basal to apical locations when feasible (see figures 4, 5 and 6). A lateral LAO, RAO and/or AP fluoroscopy screen shot will be taken to document the different (temporary) electrode positions. A marker is placed on the xyphoid to register the fluoroscopy images.

A Millar pressure catheter or similar will be introduced via the femoral artery retrograde across the aortic valve into the LV for hemodynamic pressure monitoring. Heparin will be administered to ensure that the activated clotting time is monitored per standard hospital practice.

The following LV pacing configurations will be evaluated:

Biventricular pacing (BiV)

Pacing will be performed on one LV electrode pair, (at 3 different longitudinal locations), and on the tip of the RV-lead. In total, three different pacing BiV settings will be evaluated.

Configuration 1: RV + LV lateral Apex

Configuration 2: RV + LV lateral Mid

Configuration 3: RV + LV lateral Base (**Reference: Standard CRT**)

MultiSpot simultaneous LV-ventricular pacing (MultiSpot-SYN)

Pacing will be performed on 3 electrodes on the LV wall, placed at different longitudinal locations, and on the tip of the RV-lead simultaneously.

Configuration 4: RV + LV lateral Apex + LV lateral Mid + LV lateral Base

MultiSpot sequential LV-ventricular pacing (MultiSpot-SEQ)

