## 7.2. General Methodology

Data summaries for categorical data will be summarized as count, e.g., number of patients, and/or number of events, and a percentage relative to the total number of patients/events. The denominator will be explicitly identified when not clear from the context. Continuous variables will be represented by mean and standard deviation, except when the distribution of the variable is highly skewed in which case median and quartiles will be reported.

P-values for hypothesis testing will be evaluated based on two-sided testing using significance level of 0.05 except for the non-inferiority testing (secondary objective 1) which is evaluated using one sided testing and a significance level of 0.025. Confidence intervals will be reported as two-sided 95% confidence intervals.

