### 7.4. Handling of Missing Data and Dropouts

No imputation of missing data is planned. Study attrition of subjects will be summarized (see Section 7.1.1). For the EP study data, it can happen that a configuration cannot be applied for a certain subject or that the data collected cannot be used for analysis. For each configuration, the number of patients with this configuration available will be summarized in a table similar to Table 3. For each objective and comparison between configurations, the number of patients effectively contributing to the analysis will be reported.

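### The kappa analysis for secondary objective 3 has no rule for patients who lack some pacing configurations, so kappa = 0 need not mean chance agreement

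*SAP*

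**What the plan says.** SAP section 7.9.5.3 A defines the rating for each patient and each measure: "Determine the best configuration for each patient, i.e., the configuration with largest maximum response". The agreement between the rating from LV dP/dt max and the rating from each other measure is then "evaluated and tested with an unweighted Kappa statistic". The SAP explains that "a kappa statistic of 0 indicates that the agreement is due to chance", and Table 19 is a shell for the test of kappa = 0 with one-sided and two-sided p-values. On who enters the analysis, section 7.9.5.3 B says only: "The analysis will be performed on patients in the analysis cohort".

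Three other parts of the plan bear on this.

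- SAP section 7.4 foresees gaps: "it can happen that a configuration cannot be applied for a certain subject". No imputation is planned.
- For primary objectives 1 and 2 and secondary objective 1, the corresponding paragraphs (7.9.1.3 B, 7.9.2.3 B, 7.9.3.3 B) add an availability rule. For secondary objective 1, for example, "it is necessary that patient have measurements during MultiSpot SEQ and SYN pacing".
- The cohort definition does not close the gap. Protocol section H.1 required a successfully completed EP procedure. SAP sections 7.1.3 and 7.12 put a limit on the time between MRI and EP visit in its place.

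**The concern.** In a patient with all five configurations and no preference among them, two unrelated measures pick the same one 1 time in 5. In a patient with only two configurations they agree 1 time in 2. Kappa subtracts a single chance term computed from the pooled five-category margins. When the two kinds of patient share one table, that term is too small for the mixture, and the expected kappa is above zero although the measures are unrelated within every patient. The SAP's reading of a zero kappa then fails.

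Missing configurations may also come in groups. Protocol section F.2.2 plans electrode positions "covering the LV basal to apical locations when feasible", and configurations 1, 4 and 5 as listed all use the apical electrode. One access failure could therefore remove three of the five categories, for both measures at once.

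At stake is the study's evidence on whether non-invasive sensors can help to choose a pacing configuration. The error runs in one direction, towards making an uninformative sensor look useful.

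**Working it through.** **1. The plan's own figures.** Tables 18 and 19 are shells with placeholder values: kappa 0.3449, standard error 0.0724, null standard error 0.0612. Then Z = 0.3449 / 0.0612 = 5.636 (5.6366 stated; the difference is rounding), and the interval is 0.3449 ± 1.96 × 0.0724 = 0.2030 to 0.4868, as stated. This confirms only that the ordinary large-sample kappa test is meant.

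**2. Inputs.** Up to 40 patients (SAP section 7.1.1). Five categories. For the test, "P-values for hypothesis testing will be evaluated based on two-sided testing using significance level of 0.05". The number of patients with missing configurations, and which ones they miss, is not in the documents and is varied below. *Unrelated* means that the two ratings are independent within a patient, given the configurations available in that patient.

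**3. Closed form.** Suppose a fraction f of patients has only BiV mid and BiV basal, and all available configurations are equally likely to be best. Take f = 6/40 = 0.15.

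- Observed agreement: 0.85 × 0.20 + 0.15 × 0.50 = 0.245.
- Margins: 0.85 × 0.20 = 0.17 for each of apical BiV, SYN and SEQ; 0.17 + 0.15 × 0.50 = 0.245 for each of mid and basal.
- Chance term: 3 × 0.17² + 2 × 0.245² = 0.20675.
- Kappa: (0.245 − 0.20675) / (1 − 0.20675) = 0.048.

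Now let SYN and SEQ each be best in 35% of complete patients and the three BiV configurations in 10% each, on both measures. This is in line with the hypothesis that MultiSpot pacing is superior.

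- Agreement in complete patients: 3 × 0.10² + 2 × 0.35² = 0.275.
- Observed agreement: 0.85 × 0.275 + 0.15 × 0.50 = 0.30875.
- Margins: 0.085 apical; 0.085 + 0.075 = 0.16 each for mid and basal; 0.2975 each for SYN and SEQ.
- Chance term: 0.085² + 2 × 0.16² + 2 × 0.2975² = 0.2354.
- Kappa: (0.30875 − 0.2354) / (1 − 0.2354) = 0.096.

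**4. Rejection rate.** Simulation with N = 40, unrelated ratings, unweighted kappa with its null standard error, and |Z| > 1.96:

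| Configurations lost | Patients affected | Two-sided rejection |
|---|---|---|
| None | 0 | 5.4% to 5.5% |
| 1, 4 and 5 | 2 of 40 | 6.4% (equal preference); 8.1% (MultiSpot favoured on both measures) |
| 1, 4 and 5 | 6 of 40 | 10.6% (equal); 15.2% (favoured on dP/dt max only); 22.2% (favoured on both) |
| 1 and 4, SEQ still delivered | 6 of 40 | 7% to 8% |
| 1 only | 6 of 40 | 5% to 6% |
| One at random | 6 of 40 | 5.7% to 5.9% |

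The upper figure depends on how strongly MultiSpot is favoured. Modelling it as 1 SD better on both measures, instead of the 35% split, gives 25.0% in the 22.2% cell.

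**5. After the fix.** With the same 40 patients limited to the 34 complete ones, mean kappa is about 0 and rejection is 5.2% to 5.6%.

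**The case against.** The strongest objection is that the material figures rest on one severe pattern of loss, which the documents do not establish. Protocol section F.2.2 speaks of pacing at up to three LV electrodes, and both documents let the number of spots in the sequential configuration depend on measured delays. SEQ, and perhaps SYN, might therefore be delivered without the apex. The protocol also provides other ways to reach the apex, such as another vein, a small catheter or a guide wire. This stands: under the milder patterns the inflation is small or absent. The listed configurations 4 and 5 do name the apex, however, so the severe pattern cannot be excluded.

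A reader might take the increase from 34 to 40 patients (SAP section 6.1) as the plan's forecast that 15% will lack configurations. It is not. It covers all data collection problems, including unusable recordings that yield no rating and cause no bias. Here 15% is only an illustrative anchor.

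A reader might also infer that the SAP deliberately includes incomplete patients. It is silent on them, and silence leaves the whole cohort in. Section 7.4 promises the number contributing to each objective, and section 7.9.5.3 A the number available. That would make the problem partly visible, but neither section defines availability as all five configurations.

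Finally, section 7.9.5.1 specifies no hypothesis, and the study is described as exploratory. In the equal-preference case the bias of 0.05 is smaller than kappa's sampling SD of about 0.08. This limits the consequence. The SAP nevertheless plans the test and its p-values.

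**Conclusion.** The point holds as a conditional one. As written, the plan mixes patients with different choice sets in one kappa table, and the test of kappa = 0 is then no longer a test of chance agreement. The direction is certain for unrelated measures whose preferences are equal, and it was the same in every pattern of loss examined.

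The size rests on two assumptions that the documents do not settle: how many patients lack configurations, and which ones. If loss of the apical electrode removes configurations 1, 4 and 5, rejection is about 6% to 8% with 2 of 40 affected and 11% to 22% with 6 of 40, with mean kappa about 0.05 to 0.10 in the latter case. The upper end also needs both measures to favour MultiSpot pacing. If SEQ survives it is 7% to 8% at 6 of 40, and if only apical BiV is lost it is essentially nominal.

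The documents do not support the unconditional reading that the analysis will give false positives. Nor do they support any effect on the primary objectives or secondary objective 1, which carry their own availability rules.

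**What to change.** Add to SAP section 7.9.5.3 B: *For each measure, the kappa analysis includes patients with all five configurations available for both LV dP/dt max and that measure; the number included and excluded is reported.* A rule for each measure is needed in any case, because non-invasive blood pressure is collected only optionally.

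To use all patients, a permutation test of kappa = 0 stratified by the set of available configurations may be added as a sensitivity analysis. One measure's ratings are permuted only among patients who share the same set.

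The cost is one sentence, fewer patients and a wider interval in an exploratory table. With 6 of 40 excluded (15%) the interval widens by roughly √(40/34) = 1.08, about 8%. With 12 of 40 excluded (30%) it widens by √(40/28) = 1.20, about 20%. The result then describes only patients in whom all five configurations were available.
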